- A. standard dose (90mg twice daily of ticagrelor) for 7-10 days (phase 1) and then cross-over to low dose (60mg twice daily of ticagrelor) for 7-10 days (phase 2)
- B. low dose (60mg twice daily of ticagrelor) for 7-10 days (phase 1) and then cross-over to standard dose (90mg twice daily of ticagrelor) for 7-10 days (phase 2).

After the 2 phases of treatment (maximal treatment period 20 days) patients will resume their standard DAPT with aspirin and clopidogrel (end of study treatment).

[figure not shown]
After 7-10 days of treatment, patients will come for their blood sampling in the morning hours. In particular, patients will not assume their scheduled morning dose of study medication to allow assessment of trough levels of platelet reactivity. Patients will be administered the dose of the randomized treatment while at the clinic and blood sampling will be collected after 2 hours

in order to assess peak levels of platelet reactivity. After completing the first phase of the randomized assignment, patients will initiate the second phase and start assuming assigned medication 12 hours the last dose.

Blood for sampling will be collected at the following visits (a total of 5 assessments at 3 visits):

- a) baseline (24 hours after last clopidogrel MD): PD assessments
- b) after 7-10 days of ticagrelor therapy (phase 1-pre-crossover): PK and PD assessment will be assessed to define trough (12 ± 2 hours after last ticagrelor dose) and peak (2 hours after ticagrelor administration) activity
- c) after 7-10 days of ticagrelor therapy (phase 2-post-crossover): PK and PD assessment will be assessed to define trough (12 ± 2 hours after last ticagrelor dose) and peak (2 hours after ticagrelor administration) activity.

A flow diagram of the study is presented below.

Blood sampling: Peripheral venous blood samples (20 mL) will be drawn through a short venous catheter inserted into a forearm vein and collected in citrate and serum tubes as appropriate for assessments. The first 2-4 mL of blood will be discarded to avoid spontaneous platelet activation.

Laboratory assessments

1. Whole blood vasodilator-stimulated phosphoprotein (VASP)
2. VerifyNow P2Y12 point of care testing
3. Light-transmittance aggregometry (LTA)
4. Thromboelastography
5. Reticulated Platelets (RPs)

6. Serum thromboxane B2
7. PK assessment

Description of laboratory assays

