- 7) *Pharmacokinetic (PK) assay*: Determination of plasma concentration of ticagrelor and its active metabolite (AR-C124910XX) will be assessed from blood samples taken at the same time points of PD analysis as previously described [40]. Blood samples for measurement of drug concentrations will be drawn through the same cannula used for PD sampling. The blood will be taken into lithium heparin tubes and placed on ice until centrifugation (2800 rpm, 4°C, 10 min) within 30 min of sampling to collect the plasma, which will be transferred to plain polypropylene tubes and frozen upright at or below -20°C until analysis.

Primary and secondary objectives

The primary end point is the level of on-treatment platelet reactivity as assessed by VASP-PRI after treatment with ticagrelor 90mg bid on top of aspirin (81mg/day) for 7-10 days. The primary hypothesis of our study is that in DM patients the presence of CKD is associated with lower platelet inhibition (assessed by PRI determined by VASP-P) compared with those without CKD.

Additional objectives include:

- 1) The comparison of PD measures following administration of ticagrelor 90 mg between CKD and non-CKD groups at each time point assessed with PRU determined by the VerifyNow P2Y12 assay, 5 and 20 µM ADP-induced platelet aggregation by LTA and clot kinetic assessed by CORA[®] system.

- 2) The comparisons of level of platelet reactivity as assessed by multiple assays after treatment with ticagrelor 60 mg bid (on top of aspirin 81mg/day) for 7-10 days between the CKD and non-CKD groups.
- 3) The comparison of plasma concentrations of ticagrelor and its metabolite between the DM patients with and without CKD after 7-10 days of ticagrelor (60 and 90 mg) treatment.
- 4) The comparison of platelet inhibition by standard dose (90mg twice daily) versus low dose (60mg twice daily) of ticagrelor in DM patients with or without CKD.
- 5) The comparison of the rates of high on-treatment platelet reactivity (HPR), defined as VASP-PRI $\geq 50\%$, PRU > 208 , 5 μM ADP-induced maximal platelet aggregation $\geq 46\%$ or ADP induced MA > 47 (41,42).
- 6) To evaluate whether response to ticagrelor varies with the proportion of RPs in DM patients according to the CKD status.
- 7) To assess the effects of different levels of P2Y₁₂ inhibition with thromboxane levels.
- 8) The comparison of PD and PK measures according to the CKD classification based on markers of kidney damage (ACR).

Sample Size Computation and Power Analysis

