
The primary hypothesis of our study is that in DM patients the presence of CKD is associated with lower platelet inhibition compared with those without CKD after administration of ticagrelor 90 mg bid. Under the assumption of 10% absolute difference in mean PRI between CKD and non-CKD groups, with a common standard deviation of 13.0% a sample size of 37 patients per group will allow to detect a difference in platelet aggregation between the two

cohorts with a 90% power and two-sided $\alpha=0.05$ (22). Considering the two cohorts (CKD and non-CKD), 74 patients with a valid primary end point data will be needed. Assuming a 40% rate of invalid results due to hemolysis or drop-out, up to 102 patients will need to be randomized in the study. We anticipate to consent approximately 115 patients in order to reach the target number of patients. We have chosen a 10% absolute increase of PRI by VASP-P as reference value since this has been associated with a difference in clinical outcomes (43).

Statistical analysis plan

Categorical variables will be expressed as frequencies and percentages. Continuous variables will be presented as mean \pm SD or median [IQR] when appropriate. Continuous variables will be analyzed for normal distribution with the Kolmogorov-Smirnov test. Student's t-test will be used for comparison of normally distributed continuous variables. Wilcoxon test or Mann-Whitney's U test will be used for comparisons of continuous variables not following a normal distribution. An analysis of covariance (ANCOVA) method with a general linear model, using baseline variables significantly different between groups as covariates, will be used to evaluate the overall difference between groups and all between-groups comparisons, in line with other PK and PD studies (22,24). Analysis of variance (ANOVA) will be used to evaluate intragroup comparisons. In line with recommendations for cross-over study designs, treatment effects will be evaluated considering the functional parameters observed in the overall patient population after the treatment regardless of the sequence in which patients received treatment. Patients who will successfully complete at least one treatment phase of the study will be considered for comparisons. The absolute between-treatment mean differences and 95% confidence intervals will be estimated in the two groups. In order to perform an unbiased

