estimation of the treatment effect, period and sequence effects, which may occur in crossover studies, will be evaluated. A p-value <0.05 will be considered statistically significant. Statistical analysis will be performed using a SPSS v22.0 software.

Publication Strategy/Additional Information

This study will be performed at the University of Florida Health Science Center at UF Health - Division of Cardiology. Patients will be recruited and consented at the Cardiology clinics in the UF Health system. Patients will be screened by cardiology research, who will verify that all candidates meet inclusion criteria. Subjects will be identified with a number and data collection sheets will all be stored in a locked area. Data will be kept for 6 years after enrollment ends to comply with HIPAA regulations. Patients will receive a handout with the names and telephone numbers of the doctors involved in the study. Patients will sign an informed consent relating to the study. Study subjects will be identified first (months 1-18): we expect to enroll 4-5 subjects monthly and complete enrollment in 18 months (total: 82 subjects enrolled). Months 19-20 will be implied for statistical analysis and months 21-22 for manuscript preparation.

We anticipate no major problems with the described protocol since the approach is a straight forward prospective study and is based on well-established methods. However, since there is limited experience with to define platelet function in this specific subset, variability may be higher than expected and we cannot currently perform a detailed sample size calculation. We anticipate adding this to the protocol after inclusion of the study population has been completed. If the sample size after one year is estimated to be too small, additional patients will be included. This approach is in agreement with recommendations for pilot investigations (44).

Possible Discomforts and Risk

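### The CKD versus non-CKD comparison of drug concentrations has no planned exposure ratio or confidence interval, and its ANCOVA has no stated log transformation

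*Combined protocol and SAP*

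**What the plan says.** Objective 3, under Primary and secondary objectives, is "The comparison of plasma concentrations of ticagrelor and its metabolite" between diabetic patients with and without CKD, after 7-10 days at each dose. It names no scale, summary measure or model. Research design sets the sampling: in each phase, "PK and PD assessment will be assessed to define trough" and peak values.

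The Statistical analysis plan has no paragraph on concentrations. Its general rules are:

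- Continuous variables are summarised as mean and SD, or median and IQR.
- A Kolmogorov-Smirnov test decides between Student's t-test and a Wilcoxon or Mann-Whitney test.
- An ANCOVA, with covariates chosen because they differ significantly between groups at baseline, "will be used to evaluate the overall difference between groups and all between-groups comparisons".
- "The absolute between-treatment mean differences and 95% confidence intervals will be estimated in the two groups".
- "A p-value <0.05 will be considered statistically significant".

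Log transformation, geometric means and ratios of exposure are not mentioned.

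**The concern.** Study aims names the effect of CKD on the pharmacokinetic profile of ticagrelor as part of the main question. The natural answer is a ratio: exposure in CKD patients is so many times that in non-CKD patients, with an interval. Neither branch of the gated test is planned to give this. Mann-Whitney gives a p-value, and the t-test compares arithmetic means.

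The ANCOVA matters most. The CKD groups are formed by GFR, not by randomisation, so the adjusted comparison carries the weight. The normality check selects between the unadjusted tests only; the ANCOVA has no alternative for skewed data. Plasma concentrations are positive and commonly spread in proportion to their level, in which case a linear model on the untransformed value is inefficient.

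The interval matters because a null result is plausible. Significance and Rationale says that ticagrelor clearance depends little on renal function. A non-significant p-value alone cannot separate no relevant effect of CKD on exposure from too few patients to tell.

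**Working it through.** **Inputs from the documents.** 37 evaluable patients per CKD group, from the sample size section, which is written for VASP-PRI with "90% power and two-sided" α of 0.05. No power, SD or CV is given for concentrations.

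**The plan's own figure.** With difference 10 and SD 13, n = 2(1.960 + 1.282)² × 13² / 10² = 2 × 10.51 × 1.69 = 35.5, so 36 per group. The noncentral t gives 89.6% power at 36 and 90.4% at 37. The stated 37 reproduces.

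**Assumptions added here.** Concentrations are log-normal with the same CV in both groups and log-scale SD σ = √ln(1 + CV²). This gives σ = 0.385, 0.555, 0.703 and 0.833 at CV 40, 60, 80 and 100%. The true CKD/non-CKD ratio is 1.4. The ANCOVA has one baseline covariate that differs by 0.5 SD between groups and has log-scale correlation 0.3 with concentration; the ratio of 1.4 is at a fixed covariate value.

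**Adjusted comparison: simulated power, 37 per group.** Ranges show the spread over repeated simulations.

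| CV | ANCOVA, untransformed | ANCOVA, log | Loss (points) |
|---|---|---|---|
| 40% | 94-95% | 96-97% | about 1-2 |
| 60% | 66% | 73-74% | 7-8 |
| 80% | 43% | 53-54% | 10-11 |
| 100% | 30% | 42% | 12 |

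Type I error was 4-5% for both models.

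**Unadjusted comparison under the plan's gate, same ratio.** The plan does not say whether the Kolmogorov-Smirnov test uses Lilliefors critical values, so both versions were run.

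| CV | Gate, uncorrected | Gate, Lilliefors | t-test on log | Loss (points) |
|---|---|---|---|---|
| 40% | 94.6% | 95.1% | 95.9% | 1.3 / 0.8 |
| 60% | 69.4% | 70.7% | 72.7% | 3.3 / 2.0 |
| 80% | 50.4% | 51.0% | 53.4% | 3.0 / 2.4 |
| 100% | 38.7% | 38.4% | 40.1% | 1.4 / 1.7 |

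Over other ratios the loss stayed at about 1-4 points, and type I error of the unadjusted methods was 4.4-5.5%. The loss is small because ranks do not change under a log transform, so little is given up whenever the gate chooses Mann-Whitney.

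**What a log-scale analysis would report.** The unadjusted 95% CI for the geometric mean ratio is the estimate multiplied and divided by exp(t × σ × √(2/37)), with t = 1.993 on 72 degrees of freedom and √(2/37) = 0.2325. The factor is 1.20, 1.29, 1.39 and 1.47 at CV 40, 60, 80 and 100%. For an observed ratio of 1.0, the interval would run from 0.84 to 1.20 at CV 40%, and from 0.68 to 1.47 at CV 100%.

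**The case against.** The strongest reply is that the plan does provide for skewed data through the Mann-Whitney branch, and that the documents never say concentrations will be analysed untransformed; that is inferred from silence. A reader would also see group medians and could form a crude ratio. The objective is one of eight additional ones and is not powered. All the power figures rest on assumed CVs.

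Much of this stands. A reader might infer a general loss of power from raw-scale testing, but under the gated rule the loss is only about 1-4 points. The larger loss applies to the ANCOVA, where the reading from silence is strongest because no alternative is given. Medians yield no interval and no adjustment for baseline differences between non-randomised groups.

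Three stronger readings are tempting, and the documents do not support them:

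- *The plan chooses an absolute difference for the CKD contrast.* The sentence on absolute differences concerns differences between treatments, most naturally 90 mg versus 60 mg within each CKD group. For CKD versus non-CKD concentrations the plan names no effect measure at all.
- *The 1.5-fold dose difference makes variances unequal.* Objective 3 compares CKD groups after each dose; nothing indicates that the doses are pooled.
- *A model comparing concentrations between 90 mg and 60 mg is missing.* The dose comparison in objective 4 is of platelet inhibition.

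**Conclusion.** The point holds in a limited form. For CKD versus non-CKD concentrations of ticagrelor and AR-C124910XX, no exposure ratio or confidence interval is planned, and the ANCOVA assigned to the contrast has no stated transformation. The missing estimate is the main defect and does not depend on any assumed CV.

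The power loss is secondary. It is negligible at a CV of 40% and reaches 12 points at 100%, given log-normal data, a ratio of 1.4, 37 per group with valid concentrations, and the assumed covariate. The documents cannot show where in that range the trial lies. Validity is not in question, since type I error stays near 5% under every method. Neither the primary VASP-PRI analysis nor its sample size is affected.

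**What to change.** Add a short paragraph on concentrations to the Statistical analysis plan. Fit the planned linear model or ANCOVA to log-transformed concentrations of ticagrelor and AR-C124910XX, separately for trough and peak and separately at 60 mg and 90 mg. Back-transform the CKD coefficient and report the CKD/non-CKD geometric mean ratio with its 95% CI, alongside geometric means by group. Since zero has no logarithm, the same paragraph should say how values below the quantification limit enter.

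The cost is a few sentences and a log transform in the software already named. No new samples, visits or patients are needed. Fixing the scale in advance also removes a choice that would otherwise be made after the data are seen.

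### With the plan's own 40% loss, 74 evaluable patients require 124 randomised, not 102; if that loss occurs, 102 gives about 84% power, not 90%

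*Combined protocol and SAP*

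**What the plan says.** The section Sample Size Computation and Power Analysis sets out a chain of linked figures.

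- **Effect and spread:** "Under the assumption of 10% absolute difference in mean PRI between CKD and non-CKD groups", "with a common standard deviation of 13.0" percent.
- **Evaluable patients:** 37 per group at 90% power and two-sided 5% significance, so that "74 patients with a valid primary end point data will be needed".
- **Loss and number randomised:** "Assuming a 40% rate of invalid results due to hemolysis or drop-out, up to 102 patients will need to be randomized in the study".
- **Number consented:** "We anticipate to consent approximately 115 patients in order to reach the target number of patients".

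The Statistical analysis plan names Student's t-test for normally distributed continuous variables. Under Publication Strategy/Additional Information, the timeline gives a different total, 82 enrolled. That section also says that a detailed sample size calculation is not yet possible and that patients may be added if the number looks too small after one year.

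**The concern.** The number randomised has to be large enough that, after the assumed loss, the evaluable number is still there. Sixty percent of 102 is well below 74, so the stated loss, the stated number randomised and the stated power cannot all be true.

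The primary comparison is the one affected. The plan chose a 10-point difference in PRI because it links a difference of that size to clinical outcomes. If the planned loss occurs, the chance of missing such a difference is about 16%, against the roughly 10% that a reader of the protocol would take from it.

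**Working it through.** **Inputs**, all from Sample Size Computation and Power Analysis: difference δ = 10 points, common SD σ = 13, two-sided α = 0.05, power 90%, 37 per group, loss 40%, 102 randomised, 115 consented.

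**1. Reproduce the evaluable number.** For a two-sample t-test the noncentrality is δ / (σ√(1/n₁ + 1/n₂)), with n₁ + n₂ − 2 degrees of freedom.

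- 36 per group: 89.6% power.
- 37 per group: 10 / (13 × √(2/37)) = 3.31 on 72 degrees of freedom, 90.4% power.

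So 37 is the smallest group size that reaches 90%, and 74 in total is confirmed. (The normal approximation gives 36 per group.)

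**2. Inflate for loss.** Number randomised = evaluable / (1 − loss) = 74 / (1 − 0.40) = 123.3, so 124 (62 per group). The stated 102 is 22 short.

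**3. Find the loss that 102 allows for.** 1 − 74/102 = 28/102 = 27.5%. A loss of 27% gives 74/0.73 = 101.4, so 102.

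**4. Look for a route to 102.** Multiplying by 1.4 instead of dividing by 0.6 gives 74 × 1.4 = 103.6, so 104. Doing this per group and rounding down gives 37 × 1.4 = 51.8, cut to 51, and 2 × 51 = 102. That may be where the figure came from. It is still not a valid allowance, because the 40% is lost from those randomised and not from the 74.

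**5. Power if 40% are lost.**

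| Starting number | Evaluable after 40% loss | Power (t-test) |
|---|---|---|
| 124 randomised | 74 | 90% |
| 102 randomised | 102 × 0.60 = 61.2, about 61 (30 and 31) | 84.0% |
| 115, if the loss is applied to those consented | 115 × 0.60 = 69 | 88% |
| 82, the timeline total | 82 × 0.60 = 49.2, about 49 | 75% |

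The result for 102 depends little on the exact split: 83.4% at 30 and 30, 84.6% at 31 and 31. The normal approximation gives 85.3%.

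**6. Detectable difference.** At 90% power it is 11.07 points with 30 per group and 10.88 with 31 per group, against the planned 10.

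**The case against.** - **The 40% is a planning assumption, not a forecast.** If no more than about 27% are lost, 102 is enough and the 90% stands. A patient also enters the comparisons after completing a single treatment phase, which may reduce the loss. This is true, and the 84% is conditional on the 40%. But the primary end point needs a valid VASP result on the 90 mg dose, and 40% is the plan's own allowance for not having one. If less is expected, the plan should say so.
- **The plan already allows patients to be added.** The clause under Publication Strategy/Additional Information does provide a route. It is prompted by variability higher than expected and a look after one year, so it does not correct the loss allowance.
- **The loss of power is modest.** It is about 6 points, in a single-centre pharmacodynamic study that cites pilot-study guidance and is not designed to show clinical benefit. Power stays above 80% until about 45% of 102 are lost (28 per group, 80.7%). This is fair as a comment on the consequence, and 84% may well be acceptable. It does not make the stated 90% correct.
- **The 27% is only a back-calculation.** Nothing in the documents supports it as the intended loss, and the per-group uplift is the simpler explanation of 102. This stands, so restating the loss is legitimate only if the sponsor can justify the lower rate.

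**Conclusion.** The concern holds. The evaluable target of 74 is right, and the step from 74 to 102 is wrong. At a 40% loss the number randomised must be 124. With 102, about 61 patients are evaluable, 13 below the target, and power is about 84%, some 6 points under the stated figure. No reading of the section rescues 102: the phrase "Assuming a 40% rate of invalid results due to hemolysis or drop-out, up to 102 patients will need to be randomized in the study" sets a ceiling, so it adds no margin, and even all 115 consented fall short of 74.

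The power figures rest on the plan's δ of 10 and SD of 13, a two-sample t-test, near-equal groups and the full 40% loss. The need for 124 rests only on the 74 and the 40%. Because this is the justification for the primary comparison, it must be corrected, although the effect on the study is moderate.

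**What to change.** Choose which figure gives way and restate the others to match:

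1. **Keep 102 and 40%.** State that about 61 patients would be evaluable, with about 84% power for a 10-point difference. This costs one sentence and no patients, but the stated power is lower.
2. **Keep 102 and 90%.** State a loss of about 27% and give the grounds for it. This also costs one sentence and no patients, but it is open only if the lower rate is credible.
3. **Keep 40% and 90%.** Randomise 124 and raise the number consented above that. This means 22 more randomised patients. At the planned 4 to 5 enrolled per month that is roughly 4 to 6 months more (22/5 = 4.4; 22/4 = 5.5).

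The first is the cheapest. Whichever is chosen, bring the 82 enrolled and the statement that no detailed calculation is yet possible, both under Publication Strategy/Additional Information, into line with the sample size section. This needs a second short edit.

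### The primary CKD comparison can use only patients with a valid 90 mg VASP-PRI, although 40% loss is expected and 60 mg PRI from the same patients could recover up to about 5 points of power

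*Combined protocol and SAP*

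**What the plan says.** The section on primary and secondary objectives makes VASP-PRI after 7-10 days on 90 mg twice daily the primary end point. It does not say whether the trough or the peak sample is meant, although the research design takes both on each dose.

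The sample size section starts from a stated effect, "Under the assumption of 10% absolute difference in mean PRI between CKD and non-CKD groups", and continues "with a common standard deviation of 13.0% a sample size of 37 patients per group", for 90% power at two-sided 0.05. It concludes that "74 patients with a valid primary end point data will be needed". It then allows for loss, "Assuming a 40% rate of invalid results due to hemolysis or drop-out", and arrives at "up to 102 patients will need to be randomized in the study". The 40% is not divided between spoiled samples and lost patients.

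For group comparisons the statistical analysis plan names Student's t-test, a rank test for non-normal data, and ANCOVA by general linear model. ANOVA is named for comparisons within groups. On who is analysed it says: "Patients who will successfully complete at least one treatment phase of the study will be considered for comparisons". It names no imputation, no likelihood-based repeated-measures model and no other way of handling missing values.

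**The concern.** A t-test, rank test or ANCOVA with 90 mg PRI as the outcome has no place for a patient without that value. A baseline covariate in the ANCOVA does not bring such a patient back. The inclusion rule appears to keep a patient who completed only the 60 mg phase, or whose 90 mg sample was spoiled, but nothing says how that patient would inform the 90 mg comparison.

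The design nevertheless collects information on such patients. Each patient is due to give PRI on both doses, and the two values are likely to be correlated. If a single 90 mg sample is lost to haemolysis, the 60 mg value still says something about what the 90 mg value would have been. With two fifths of primary results expected to be lost, precision is at stake. So is a clear statement of what the analysis assumes about the missing values.

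**Working it through.** **Inputs from the documents:** difference 10 points, SD 13, two-sided 0.05, 37 valid per group, 102 randomised, 40% loss. **Assumed, because the documents are silent:** equal groups of 51, correlation ρ between 90 mg and 60 mg PRI of 0.3 to 0.7, the same 40% loss on the 60 mg dose, and the share of loss that takes the whole patient.

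**1. The plan's own figure.** Power comes from the noncentral t with 2n − 2 degrees of freedom and noncentrality 10 / (13 × √(2/n)).
- n = 37: noncentrality 3.31, power 90.4%.
- n = 36: power 89.6%.

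The 37 per group is reproduced.

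**2. Complete-case power with the planned numbers.** 102 × 0.6 = 61.2 valid values, or 30.6 per group. Noncentrality is 10 / (13 × √(2/30.6)) = 3.01 and power is 84.1%.

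**3. Where the shortfall comes from.** Keeping 74 valid values after 40% loss needs 74 / 0.6 = 123.3, so 124 randomised. That leaves 37.2 per group and complete-case power of 90.5%. The stated 102 allows for a loss of only 1 − 74/102 = 27.5%.

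**4. What the 60 mg PRI can add.** Let b be the patients per group with both values and a the number with only one of them (the same for each dose). The maximum-likelihood 90 mg mean is then worth

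n_eff = A − (bρ/(1 − ρ²))² / A, with A = b/(1 − ρ²) + a.

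If a share f of the 40% loss takes whole patients, let L = 0.4f. The remaining single-sample loss rate is s = 1 − 0.6/(1 − L), taken as independent for the two doses, so b = 51(1 − L)(1 − s)² and a = 51(1 − L)s(1 − s).

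Example with f = 0 and ρ = 0.7: b = 18.36, a = 12.24, A = 36 + 12.24 = 48.24, and n_eff = 48.24 − 25.2²/48.24 = 35.1 per group. Power rises from 84.1% to 88.8%.

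| Loss pattern | b, a per group | ρ = 0.3 | ρ = 0.5 | ρ = 0.7 |
|---|---|---|---|---|
| All single samples | 18.4, 12.2 | 84.9% | 86.4% | 88.8% |
| Half whole patients | 23.0, 7.7 | 84.8% | 85.9% | 87.6% |
| Three quarters whole patients | 26.2, 4.4 | 84.5% | 85.3% | 86.4% |
| All whole patients | 30.6, 0 | 84.1% | 84.1% | 84.1% |

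The gain is therefore 0 to 4.7 points. It would be larger if 60 mg values were lost less often: with a valid 60 mg PRI in every patient and ρ = 0.7, power is 91.2%. That sits badly with a 40% loss rate on the same assay.

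**5. Check with the covariance estimated.** In 3,000 simulated trials per setting, the 60 mg value was present in 60% of patients lacking a 90 mg value and in 80% of the others. Power rose from 83.5% to 86.1% at ρ = 0.5 and from 84.3% to 88.6% at ρ = 0.7. Type I error was 4.9% for both analyses at ρ = 0.5; at ρ = 0.7 it was 5.1% for complete cases and 5.3% for the joint model. Period and sequence terms were not in this simulation.

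**6. Bias.** If loss depends on CKD group alone, the values observed in each group remain a random sample of that group, so the difference in means is unbiased. A simulation with 55% loss in one group and 25% in the other gave a bias of about 0.02 points on a difference of 10. Bias requires loss related to PRI within a group.

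**The case against.** The strongest reply is that the plan already provides for complete-case analysis: it counts valid primary values and inflates for loss. With the inflation done correctly, the simple test has its 90% and the model is only an efficiency preference. The section on publication strategy also allows patients to be added if the sample proves too small. This stands as far as the cause goes. A reader might infer from the 84% that the choice of test costs the trial its power, but the documents' own figures trace the shortfall to 102 against 124.

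A reader might also infer that unequal loss between CKD and non-CKD patients would by itself bias the result. Step 6 shows that it would not. Drop-out linked to tolerability could bias it if tolerability is related to PRI within a group, but the mixed model has no tolerability variable and would not necessarily remove that bias.

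Nor does the plan throw the other data away. The 60 mg PRI and the other assays serve the secondary objectives; they are unused only in the primary group test. That this test is complete-case is itself inferred from the named methods, not stated.

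Finally, haemolysis may spoil a whole draw. The research design takes the blood for each assessment through one short catheter, so VerifyNow and aggregometry results from that visit may be affected too. This counts against imputing PRI from them. It does not affect the use of PRI from the other dose, which comes from a different visit.

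What remains is that better use of data already collected is available at little cost, and that the plan does not say how missing primary values are handled.

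**Conclusion.** The point holds as a modest, inexpensive improvement. With 102 randomised and 40% lost, complete-case power is about 84%. A likelihood-based analysis of both doses would bring it to between 84% and 89% for assumed correlations of 0.3 to 0.7, with no gain at all if every loss is a whole patient. The figures rest on equal groups, the same loss rate on both doses, normal data and values missing at random. The documents fix neither the correlation nor the loss pattern, so the gain can only be given as a range.

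It would be tempting to conclude that the model restores the planned 90%. Over this range it does not, so it cannot replace correcting the number randomised. That correction should also settle the other enrolment figure, in the section on publication strategy ("total: 82 subjects enrolled"). At 82 with 40% lost, 49.2 valid values remain and complete-case power is 75.3%.

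**What to change.** - Name trough or peak as the primary time point. Until then the 90 mg CKD contrast is not a single quantity.
- Estimate that contrast from a repeated-measures mixed model on all valid VASP-PRI values at the chosen time point from both doses, with fixed effects for CKD by dose, period and sequence. Use an unstructured within-patient covariance, not one random intercept stretched across trough and peak samples.
- Keep the complete-case t-test or ANCOVA as a sensitivity analysis.
- Report invalid and missing results by CKD group, dose and cause, with haemolysis separated from drop-out.
- Do not impute PRI from same-visit VerifyNow or aggregometry results.
- Correct 102 against 124, and reconcile both with 82, as a separate change.

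The analysis changes need SAP wording and modest work in the named software, with no extra patients or samples. The downside is reliance on a missing-at-random assumption, which the SAP should state.
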